6.4.2 Assignment of medications to study period

The following rules will be used to assign a medication to a study period:

- **Treatment Period:** a medication will be assigned to the Treatment Period if it has been taken at least once between the first administration of IMP on Day 1 of each study cycle, up to Day 43 or PEOT assessments.

- **Observation Period:** a medication will be assigned to the Observation Period if it has been taken at least once from the day after Treatment Period to the Day 155 visit of each study cycle.

The prior or concomitant medications out of the 2 periods above will be displayed as 'NA' in the listing.

7 MEASUREMENTS OF TREATMENT COMPLIANCE

Not applicable. The number of infusions will be recorded as detailed in [Section 8.1](#).

8 SAFETY ANALYSES

All safety analyses tables and figures will be presented using the SS. All listings will be presented using FAS. Listings will be presented by treatment group, study cycle, and participant; tabulations will be presented by treatment group, RLZ total and/or study cycle. Unless otherwise specified, safety analyses will be presented by actual dose received as defined in [Section 3.6](#).

8.1 Extent of exposure

The following dosing information for entire study will be summarized using SS by RLZ total:

- Number of participants receiving 7mg/kg or 10mg/kg initially and the treatment sequence (eg 7mg/kg-7mg/kg, 7mg/kg-10mg/kg, etc.)

The following dosing information for entire study will be summarized using SS by the first cycle treatment and RLZ total:

- Total number of study cycles (regardless of the first cycle being mandatory or not) as a continuous variable (n, sum, mean, sd, median, min, max will be provided)
- Number of study cycles (1, 2, 3, ..., until the maximum number of study cycles)
- Number of cycles per participant year rate
- Time in study [<3 months (90 days), >=3 to <6 months (180 days), >=6 to <9 months (270 days), >=9 to <12 months (360 days), >=12 to <24 months (720 days), >=24 months to <30 months (900 days), >=30 to <36 months (1080 days), >=36 months (1080 days)]
- Time in study (months) and time in study (days) as continuous variables (n, sum, mean, sd, median, min, max will be provided)

Note:

- Time in study=Date of last visit or withdrawal–Date of first visit+1. Time in study last category will be adjusted based on data to have non-zero count in last category.
- Number of cycles per participant year rate=(Sum of number of cycles)/(Sum of participant year), where Participant year=Time in study /365.25.
- 1 month=30 days.

The following dosing information will be summarized using SS by entire study, study cycle, actual dose received within each cycle and RLZ total:

- Number of infusions received as a continuous variable (n, sum, mean, sd, median, min, max will be provided)
- Number of infusions received by the following categories:
 - For each study cycle: 1, 2, 3, 4, 5, 6
 - For entire study: 1-6, 7-12, 13-18, 19-24, 25-30, 31-36, 37-42, 43-48, ..., until last interval where the maximum number of infusions falls into.

Notes:

- Values for entire study will be the summation from study cycles;

A figure for actual dose received in all study cycles by participant will be provided. Figures of exposure by time, by number of cycles, by drug free time for participants from MG0004, and by drug free time for participants from MG0003 will also be provided.

All IMP administration details will be listed.

8.2 Adverse events

8.2.1 Data considerations

Adverse events will be recorded from the time of informed consent until study completion. All AEs will be coded ([Section 3.8](#)).

In addition, AEs will be classified according to the Common Terminology Criteria for Adverse Events (CTCAE) Version 5 or later for severity. For any AEs where it is not possible to provide a CTCAE grading, the events will be assessed using a standard intensity classification (mild, moderate, and severe). For the purpose of reporting severe AEs, all CTCAE severity classifications will be mapped to a standard intensity classification as described below:

- Grade 1 - Mild
- Grade 2 - Moderate
- Grade 3, 4, 5 - Severe

These will be tabulated together with the AEs that were not classified according to CTCAE criteria (ie, all Grade 1 AEs as per CTCAE criteria will be included in the 'mild' category together with those AEs classified as mild as per the standard intensity classification). In the case a mapped standard intensity classification per above rule is different from the standard intensity classification on CRF, the worst case will be used as the standard intensity classification (ie, an AE with Grade 1 and moderate as intensity classification will be classified into moderate).

Any AE that occurred during the study will be defined as "**any AE**".

For each cycle, a **TEAE** is defined as any event that was not present prior to the first administration of rozanolixizumab of each treatment cycle or any unresolved event already present before the first administration of rozanolixizumab that worsens in intensity following exposure to treatment up to and including 8 weeks (56 days) after the last dose of each treatment cycle.

The following rules will be used to assign a TEAE to a study period in each study cycle:

- **Treatment Period:** a TEAE will be assigned to the Treatment Period for the tabulations if the start date of the event is on or after the date of the first administration of MG0007 IMP on Day 1, up to 7 days after the last dose of IMP in each cycle;
- **Observation Period:** a TEAE will be assigned to the Observation Period for the tabulations if the start date of the event is greater than the day after Treatment Period until 8 weeks (56 days) following the final dose in each study cycle.

An intermittent period AE is defined as AEs occurring after the 8-week (56-day) TEAE period, prior to the next cycle.

A persistent AE is defined as an unresolved AE that extends continuously from MG0003 /MG0004 to MG0007 and does not worsen in intensity following exposure to IMP in MG0007. Persistent AEs will be recorded in MG0007 database.

Where dates are missing or partially missing, AEs will be assumed to be treatment-emergent unless evidence exists that does not allow the AE to be treatment-emergent. Handling of missing dates for classification of AEs as TEAEs is described in [Section 4.2.2](#).

A TEAE will be counted as a TEAE related to IMP if the response to the question “Relationship to Study Medication” is “Related”.

AEs will be presented as “number of participants (percentage of participants) [number of events]”. In this style of output, “[number of events]” will include all cases of an AE including repeat occurrences in individual participants, while “number of participants” will count each participant only once.

Persistent AEs, intermittent period AEs and other non-TEAEs will be listed only.

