4.1.1 Study population

Study participants will enter from MG0003, or MG0004. Participants eligible for enrollment in this study completed MG0003, required rescue therapy during the Observation Period in MG0003 (except for study participants who opted to receive IVIg or PEX in MG0003), or completed at least 6 treatment visits in MG0004.

Study participants directly enrolling from MG0003 can use the EOS assessments as the Baseline (Day 1) in MG0007.

Study participants directly enrolling from MG0004 who have completed at least 6 visits regardless of the number of infusions (due to low IgG resulting in IMP treatment hold) will complete the PEOT visit (if entering from Treatment Period of MG0004) or EOS visit (if entering from Observation Period of MG0004) assessments from MG0004 and will directly enter the Observation Period (Visit 9 [Day 71]) of the initial fixed cycle.

A study participant who had to discontinue receiving treatment under the MG0003, or MG0004 due to the coronavirus disease 2019 (COVID-19) pandemic (ie, due to logistic reasons, resolution of suspected or confirmed COVID-19 infection, or fulfillment of quarantine period due to exposure) and provided no parameter(s) meeting the protocol-defined study drug discontinuation criteria can potentially enter MG0007. The Investigator should assess all available medical information prior to the study participant joining MG0007. The Investigator must discuss the eligibility for the study participant to join the MG0007 study based on a thorough individualized benefit-risk evaluation (ie, disease status, alternative options, AE profile, laboratory assessments), the regional situation, and protocol criteria and treatment schema with the Sponsor's Study Physician. Study participants with a gap of >4 weeks between the EOS visit from the lead-in study and the start of MG0007 must have an eligibility assessment performed during a 4-week Screening Period (see Section 10.11).

No formal sample size calculation can be performed. Approximately 200 study participants will be enrolled at approximately 130 sites from North America, Europe, and Asia (including Japan).

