8.3.8 Treatment-emergent adverse events

Treatment-emergent AEs are defined as AEs starting after the time of first IMP administration up to and including 8 weeks after the final dose.

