9.1 Definition of analysis sets

The definition of analyses sets are as follows:

- The Enrolled Set: All study participants who have signed the ICF.
- Full Analysis Set (FAS): All enrolled study participants who were randomized in this study or in MG0004. Study participants enrolling from MG0004 will utilize their last assigned dose level from MG0004 as their planned dose in MG0007.
- Safety Set (SS): All study participants in the FAS who received at least one dose of IMP.

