3.5.3 Safety Set

The Safety Set (SS) will consist of all study participants in the FAS who received at least one dose of IMP in MG0007.

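### AEs in MG0004 PEOT entrants that start within 56 days of the last MG0004 dose, but before any MG0007 dose, are not treatment-emergent, and reach no SAP Section 8 table if the entrant is never re-dosed

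*SAP*

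**What the plan says.** **Window.** SAP 8.2.1 anchors a TEAE to the first dose of each cycle ("any event that was not present prior to the first administration of rozanolixizumab of each treatment cycle"), adds unresolved events that worsen after dosing, and ends the window "up to and including 8 weeks (56 days) after the last dose of each treatment cycle". An event belongs to the Treatment Period if it starts "on or after the date of the first administration of MG0007 IMP on Day 1". Protocol 8.3.8 uses the same eight weeks: "Treatment-emergent AEs are defined as AEs starting after the time of first IMP administration up to and including 8 weeks after the final dose".

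**Analysis set.** SAP 3.5.3 defines the Safety Set as "all study participants in the FAS who received at least one dose of IMP in MG0007". SAP 8 adds: "All safety analyses tables and figures will be presented using the SS". Safety listings use the FAS. Protocol 9.1 defines the Safety Set as "All study participants in the FAS who received at least one dose of IMP", without naming a study, and SAP 3.9 does not mention the difference.

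**MG0004 entrants.** Protocol 2.2 describes MG0004 as weekly dosing over a 52-week Treatment Period. Under Protocol 4.1.1, its participants "will directly enter the Observation Period (Visit 9 [Day 71]) of the initial fixed cycle". Protocol 4.1 gives them a first MG0007 dose only when symptoms worsen and asks for rollover within 4 weeks of the PEOT or EOS visit. Protocol 8.3.1 collects AEs from MG0007 consent.

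**Non-TEAEs.** The end of SAP 8.2.1 confines non-TEAEs to listings. SAP 8.2.2, items 5 and 6, nevertheless plans an overview and incidence tables for them.

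**The concern.** The plan treats the 56 days after a dose as the period in which an event counts as treatment-emergent. For a participant who moves from weekly MG0004 dosing into MG0007 through PEOT, part of that period falls inside MG0007 before any MG0007 dose. The events are collected, but no rule carries the window over from the last MG0004 dose.

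The Safety Set adds a selection effect. An entrant who dies, or stops study medication permanently because of an AE, before being re-dosed never enters it. The events that prevent re-dosing are therefore the ones most exposed to loss from the serious, fatal, AESM and all-deaths summaries. At stake is the completeness of safety reporting in a study whose primary endpoints are TEAEs and TEAEs leading to IMP withdrawal.

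**Working it through.** The plan states no figure for this point. The check is a reading of the rules followed by date arithmetic.

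**Step 1: classify an example.** An AE starts 10 days after the last MG0004 dose, after MG0007 consent and before any MG0007 dose.
- TEAE under SAP 8.2.1? No, because it precedes the first dose of any MG0007 cycle. The exception is an event still unresolved that worsens after that dose.
- Intermittent-period AE? No. That category begins only after a cycle's 56-day period has ended.
- Persistent AE? No. That category requires the event to have continued from the lead-in study.
- It remains an unnamed non-TEAE.

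**Step 2: find where it is reported.**

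| Output | Entrant later re-dosed | Entrant never re-dosed |
|---|---|---|
| TEAE tables, SAP 8.2.2 items 1 to 4 (Safety Set) | No | No |
| Non-TEAE tables, SAP 8.2.2 items 5 and 6 (Safety Set) | Yes, if the listings-only sentence in 8.2.1 is overridden | No |
| All-deaths row of the overview (Safety Set) | Entrant is in the set | No |
| Discontinuation due to AEs, SAP 5.1 (FAS, with a Not Treated group) | If it led to discontinuation | If it led to discontinuation |
| FAS listings | Yes | Yes |

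Items 5 and 6 have no separate AESM table. They would also pool these events with events starting more than 56 days after a dose.

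**Step 3: days affected per entrant.** Count from the last MG0004 dose as day 0.

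Days = max(0, min(56, day of first MG0007 dose) − day of MG0007 entry)

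Inputs:
- Window: 8 × 7 = 56 days (SAP 8.2.1).
- Time from last dose to PEOT: 7 days. This is an assumption, by analogy with MG0007, where the last dose is on Day 36 and the end-of-treatment visit on Day 43 (43 − 36 = 7). Doses withheld in MG0004 would lengthen it and shrink the result.
- Rollover: 0 to 28 days after PEOT (Protocol 4.1), with consent taken at entry.
- Early re-dosing at day 28: an assumption, borrowed from the 4-week minimum between cycles in Protocol 4.1.

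| Rollover after PEOT | Entry day | Not re-dosed by day 56 | Re-dosed at day 28 |
|---|---|---|---|
| 0 days | 7 | 56 − 7 = 49 | 28 − 7 = 21 |
| 14 days | 21 | 56 − 21 = 35 | 28 − 21 = 7 |
| 28 days | 35 | 56 − 35 = 21 | 0 |

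With a gap period the overlap shrinks further: rollover 42 days after PEOT gives entry on day 49 and 7 days. Entrants from the MG0004 Observation Period contribute 0 days if their EOS visit is at least 56 days after the last dose. The documents do not give that interval.

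**Step 4: scale.** The number of MG0004 entrants, the share entering through PEOT and the share never re-dosed are not stated. For illustration only, exposed time for M PEOT entrants not re-dosed by day 56 is M × days / 365.25:
- M = 20: 20 × 21 / 365.25 = 1.1 to 20 × 49 / 365.25 = 2.7 participant-years
- M = 50: 2.9 to 6.7 participant-years
- M = 100: 5.7 to 13.4 participant-years

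**The case against.** The strongest reply is that the TEAE definition fits its objective. The primary objective is the safety of additional 6-week cycles, and Protocol 9.3.1 uses the same cycle-based window. Events that follow weekly MG0004 dosing describe another regimen. This stands: leaving them out of the primary TEAE count is not an error, and the primary tables need not change.

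A second reply is that much is already reported. SAP Amendment 2 added the non-TEAE tables, the SAP 5.1 discontinuation table covers the FAS, and every event is listed. This stands in part. A reader might infer that never re-dosed entrants appear in no safety output. The documents do not support that; the accurate statement is that they appear in no Section 8 table. Nor are all their untabulated MG0007 events drug-exposed, since some will start after day 56. But the existing outputs give no incidence by term for these entrants and do not separate carry-over events for anyone.

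Third, the words limiting the Safety Set to MG0007 can be read as clarification. Protocol 9.1 names MG0004 in the FAS definition, where earlier participation is meant to count, and not in the Safety Set definition. That is a fair reading, so a note in SAP 3.9 is good practice and not the correction of a proven departure.

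Fourth, MG0004 may report these events itself, in which case adding them to MG0007 TEAEs would risk double counting. The documents do not settle this. Protocol 2.2 says only that MG0004 closes once participants have had the chance to roll over. For ADA, by contrast, SAP 10.3.1 does count exposure across the MG studies.

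**Conclusion.** The gap is real but narrower than it may look. It concerns AEs in MG0004 PEOT entrants with onset after MG0007 consent, before the first MG0007 dose and within 56 days of the last MG0004 dose. It is most serious for entrants never re-dosed, whose serious events and deaths reach no Section 8 table.

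The reliable measure is 21 to 49 days per PEOT entrant not re-dosed by day 56, and 0 to 21 days if re-dosed at day 28. Both rest on the 7-day PEOT assumption and rollover within 4 weeks. EOS entrants probably contribute nothing. No study-wide total can be given.

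Two stronger readings should be resisted. A reader might take the top of the illustrative range, about 13 participant-years, as the loss. It needs 100 entrants, same-day rollover and no re-dosing by day 56, and none of these is documented. A reader might also infer that these events follow the longest continuous weekly dosing in the programme. Entry requires only six MG0004 visits, whatever the number of infusions, and dosing durations elsewhere in the programme are mostly not given.

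All analyses are descriptive, so no test or estimate is invalidated. This is a should-fix point about complete safety reporting.

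**What to change.** Keep the primary TEAE definition and tables. Then:

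1. In SAP 8.2.1, define a carry-over AE for MG0004 entrants: onset from MG0007 consent to the earlier of 56 days after the last MG0004 dose or the first MG0007 dose.
2. In SAP 8.2.2, tabulate carry-over AEs (any, serious, fatal, AESM, leading to permanent withdrawal) on all FAS participants from MG0004, including the Not Treated group, by last MG0004 dose level.
3. Include Not Treated FAS participants in the all-deaths count.
4. State whether MG0004 also reports these events, so that pooled safety does not count them twice.
5. Reconcile the listings-only sentence in SAP 8.2.1 with items 5 and 6 of SAP 8.2.2.
6. Note in SAP 3.9 that the Safety Set requires a dose in MG0007.

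The cost is SAP wording and one supplementary table set. No new AE collection is needed. The last MG0004 dose date must be available to the analysis; the drug-free-time figure for MG0004 participants in SAP 8.1 probably needs it already, though the SAP does not say from which dose that time runs. The downside is possible overlap with MG0004 reporting, which item 4 addresses.

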9.3 Planned safety analyses

9.3.1 Analysis of the primary safety endpoint

The frequency and severity of all TEAEs will be presented for each treatment group separately and overall by System Organ Class, high level term, and preferred term (Medical Dictionary for Regulatory Activities [MedDRA®]). The data will be displayed as number of participants experiencing the TEAE, percentage of participants, and number of TEAEs. All safety analyses will be based on the SS (Section 9.1).

For each cycle, a TEAE is defined as any event that was not present prior to the first administration of rozanolixizumab or any unresolved event already present before the first administration of rozanolixizumab that worsens in intensity following exposure to treatment up to and including 8 weeks after the last dose of each treatment cycle. Adverse events occurring after the 8-week TEAE period, prior to the next cycle, will be defined as intermittent period AEs. Any AEs that occurred during the study will be defined as "any AE".

The occurrence of TEAEs and TEAEs leading to withdrawal of IMP will be summarized for the entire study by dose at AE onset. This will include all TEAEs that occurred during and between treatment cycles.

These analyses will display the TEAEs (including any TEAEs occurring up to 1 week after the last infusion) and intermittent period AEs separately. For intermittent period AEs, the summaries will be displayed as "Off-treatment".

Further analyses will be described in the SAP.

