The rollover into MG0007 must be completed within 4 weeks after the EOS visit from MG0003, or the PEOT or EOS (as appropriate) visit from MG0004. In the event a study participant has a gap period (>4 weeks) between the EOS or PEOT visit from the lead-in study and the start of MG0007, a Screening Period of up to 4 weeks will be applicable to confirm that the study participant still meets the eligibility criteria for entry into MG0007.

Figure 2-1: MG0007 entry schema

[figure not shown]
In case of symptom worsening (eg, an increase of 2.0 points on the MG-ADL or 3.0 points on the QMG scale) between assessments, resulting in a need for additional treatment, study participants will undergo another 6-week treatment cycle followed by an Observation Period, based on the Investigator's discretion. The dose may be adjusted to 7mg/kg or 10mg/kg at the beginning of each treatment cycle based on the Investigator's discretion. The minimal time to start the next treatment cycle is 4 weeks following the last dose of the treatment period of the previous cycle. If a study participant requires treatment earlier than 4 weeks, IgG levels from the previous cycle should be considered and discussed with the Medical Monitor. A new treatment cycle **should not** be initiated until total IgG level is $\geq 2\text{g/L}$.

Participants in MG0007 will remain on their gMG background medications. With the exception of corticosteroids and acetylcholinesterase (AChE) inhibitors, all gMG medication doses should be maintained during each respective 6-week treatment cycle and efforts should be made to maintain a stable dose during the first 8 weeks of the Observation Period.

Study participants who receive rescue therapy (intravenous immunoglobulin [IVIg], plasma exchange [PEX], subcutaneous immunoglobulin [SCIg], or iv corticosteroid) during the Treatment Period are not eligible to receive any further treatment with rozanolixizumab. These participants must complete the first 8 weeks of the Observation Period after the last dose of rozanolixizumab prior to completing the EOS visit assessments, and subsequently will be withdrawn from the study.

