8.2.2 Adverse events summaries

TEAEs will be summarized by the most recent dose level prior to onset of TEAEs for entire study analysis or the highest dose within a cycle for by-cycle analysis and RLZ total including the number and percentage of study participants and frequency. Additional details are described below:

1. Overview of TEAEs by entire study and study cycle will include following categories: any TEAEs, serious TEAEs, participant discontinuation due to TEAEs, permanent withdrawal of IMP due to TEAEs, temporary withdrawal of IMP due to TEAEs, TEAEs requiring dose change, treatment-related TEAEs, severe TEAEs, TEAEs leading to death, all deaths (AEs leading to death). Additionally, summary of TEAEs by study cycle, fixed dose and weight subgroups will be conducted as specified in [Section 4.9.2](#).
2. Incidence of TEAEs will be summarized for entire study by SOC, HLT, PT for:
 - Any TEAEs
 - Any TEAEs during Treatment Period
 - Any TEAEs by maximum intensity (mild, moderate and severe)
 - Any TEAEs by relationship
 - Severe TEAEs

- Non-serious TEAEs above reporting threshold of 5% of study participants
- Fatal TEAEs
- Fatal TEAEs by relationship
- Serious TEAEs
- Serious TEAEs by relationship
- Participant discontinuation due to TEAEs
- TEAEs leading to permanent withdrawal of IMP
- TEAEs leading to temporary withdrawal of IMP
- TEAEs requiring dose change
- Treatment-emergent AESM
- Treatment-emergent AESI

3. Incidence of any TEAEs by entire study and study cycle will be summarized by decreasing participant count of PT in RLZ total. Same analysis will be repeated by fixed dose and weight subgroups as specified in [Section 4.9.2](#).

4. Incidence of TEAEs will also be summarized by SOC, HLT, PT, and the highest dose level prior to onset of TEAEs and RLZ total for each study cycle, including the number and percentage of study participants and frequency for:

- Any TEAEs
- Severe TEAEs
- Serious TEAEs
- Participant discontinuation due to TEAEs
- TEAEs leading to permanent withdrawal of IMP

5. Overview of non-TEAEs by entire study will include following categories: any non-TEAEs, serious non-TEAEs, participant discontinuation due to non-TEAEs, permanent withdrawal of IMP due to non-TEAEs, temporary withdrawal of IMP due to non-TEAEs, severe non-TEAEs, non-TEAEs leading to death.

6. Incidence of non-TEAEs will be summarized for entire study by SOC, HLT, PT for:

- Any non-TEAEs
- Severe non-TEAEs
- Serious non-TEAEs
- Fatal non-TEAEs

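### As written, each cycle's 56-day TEAE window does not stop when the next cycle starts, so an event in the overlap counts in two cycles of the by-cycle tables

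*SAP*

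**What the plan says.** SAP 8.2.1 opens a cycle's TEAE window at that cycle's first dose and runs it "following exposure to treatment up to and including 8 weeks (56 days) after the last dose of each treatment cycle". Protocol 9.3.1 has the same end point: "following exposure to treatment up to and including 8 weeks after the last dose of each treatment cycle".

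The period rules in SAP 8.2.1 repeat it. A TEAE belongs to the Treatment Period up to 7 days after the cycle's last dose, and after that to the Observation Period "until 8 weeks (56 days) following the final dose in each study cycle". The next cycle is used as a boundary in one place only: "An intermittent period AE is defined as AEs occurring after the 8-week (56-day) TEAE period, prior to the next cycle".

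SAP 2.3.1 (as protocol 4.1) sets the spacing: "The minimal time to start the next treatment cycle is 4 weeks following the last dose of the treatment period of the previous cycle". It also foresees shorter gaps: "If a study participant requires treatment earlier than 4 weeks, IgG levels from the previous cycle should be considered" and discussed with the Medical Monitor.

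For dose grouping, SAP 8.2.2 uses the most recent dose before onset in entire-study tables and "the highest dose within a cycle for by-cycle analysis and RLZ total" otherwise. Item 4 of the same section has a different by-cycle rule: "Incidence of TEAEs will also be summarized by SOC, HLT, PT, and the highest dose level prior to onset of TEAEs and RLZ total".

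**The concern.** The window runs 56 days past the last dose, while the next cycle may begin at 28 days or sooner. An event that starts or worsens on or after the next cycle's first dose and by day 56 therefore meets the definition twice: as an Observation Period TEAE of cycle k and a Treatment Period TEAE of cycle k+1. An event that starts before that dose stays with cycle k unless it worsens.

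The tables exposed are the by-cycle ones: SAP 8.2.2 items 1, 3 and 4, 8.2.3 item 2, and the Japan by-cycle table in 11.6. In 8.2.2 items 1 and 3, which group by the highest dose in the cycle, an overlap event after a dose change also appears under the earlier cycle's dose.

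The primary objective is the safety of additional cycles, and these tables are where a change in risk with repeat cycles would be looked for. A cycle followed by an early restart takes in part of the next cycle's dosing time; a cycle without one has off-dosing time there instead.

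**Working it through.** **Inputs.** Window after last dose: 8 x 7 = 56 days, as SAP 8.2.1 states. Minimum gap: 4 x 7 = 28 days (SAP 2.3.1). Six weekly infusions fall on cycle Days 1, 8, 15, 22, 29 and 36. The full window is Day 1 to Day 36 + 56, or 92 days. Of these, 43 are dosing days (to 7 days after the last dose, the 8.2.1 Treatment Period) and 92 - 43 = 49 are off-dosing days.

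**Overlap.** Count the last dose of cycle k as day 0 and let the next first dose fall on day g. Days g to 56 lie in both windows, so the overlap is 57 - g days for g up to 56, and none after that.

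| Gap g (days) | Overlap (days) | Share of 92 days | Next-cycle infusions inside cycle k's window |
|---|---|---|---|
| 21 | 36 | 39.1% | 6 of 6 |
| 28 | 29 | 31.5% | 5 of 6 |
| 42 | 15 | 16.3% | 3 of 6 |
| 56 | 1 | 1.1% | 1 of 6 |
| 57 or more | 0 | 0% | 0 |

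Example: cycle 2 starts 28 days after the last dose of cycle 1, and a new event starts on day 40. It is a cycle 1 Observation Period TEAE and also a cycle 2 Treatment Period TEAE (cycle 2 Day 13).

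**Effect on event counts.** Let r be the event rate during dosing divided by the rate off dosing. The documents do not give r, so a range is assumed. Events in an early-restart cycle relative to one without:

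((43 + overlap) x r + 49 - overlap) / (43r + 49)

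- g = 28: (72r + 20)/(43r + 49) = 1.000, 1.128, 1.215, 1.326 at r = 1, 1.5, 2, 3.
- g = 42: (58r + 34)/(43r + 49) = 1.000, 1.066, 1.111, 1.169.

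**Effect on comparisons between cycles.** If a share p of participants restart at 28 days and r = 2, the average count for that cycle is raised by p x 21.5%. Two cycles therefore differ by (difference in share) x 21.5%, relative to a cycle without restart: 2.1%, 5.4% or 10.7% for differences of 10, 25 or 50 percentage points. With equal shares the distortion is zero at any r.

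**What planned output can show.** SAP 9.11 bins the time between cycles at 21, 28 and 60 days and adds 1 day to the difference in dates. A 28-day gap is recorded as 29 and falls in the bin from 28 to 60. Gaps of 57 to 59 days, which have no overlap, fall in the same bin. The tabulation therefore bounds the share restarting within 56 days but does not give it.

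**Ending the window at the next cycle, g = 28.** The window becomes 63 days (43 dosing, 20 off). The count ratio to a full window is (43r + 20)/(43r + 49) = 0.685 at r = 1 and 0.785 at r = 2. The present excess is 29(r - 1)/(43r + 49) and the new deficit is 29/(43r + 49); they are equal at r = 2. A per-day rate still mixes dosing and off-dosing time: at r = 2 its ratio is (106/63)/(135/92) = 1.147. The Treatment Period alone is 43 against 43 days, so its ratio is 1 at any r, with no overlap for g of 8 or more.

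**Partial dates (separate, minor).** SAP 4.2.2 sets an onset known only to the month to the 1st, unless it is the month of the study's first dose. For a later cycle starting on day d of the month, such an onset can precede that cycle's first dose by d - 1 days and move to the previous cycle. It becomes a non-TEAE only if g - (d - 1) > 56, that is, g > 55 + d: more than 57 days for d = 2, 70 for d = 15, 86 for d = 31.

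**The case against.** The strongest reply is that assignment to the cycle of onset is the natural reading. SAP 3.2.2 lays out successive periods, the last ending before the next cycle. SAP 3.6 assigns entire-study events by most recent dose. The program safety analysis plan that SAP 1 relies on was not available and may hold the rule. This limits the point to the SAP wording; it does not show what the programs do. It does not close the gap: 3.2.2 runs the Observation Period to Day 155 with no stop at a new cycle, 3.6 never assigns an event to one cycle, and 8.2.1 states the 56-day end point twice.

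Other replies stand. The tables concerned are descriptive, with no testing. Without a difference in event rate and a difference in early-restart share, comparisons between cycles are not distorted. The percentages above are for event counts; SAP 8.2.1 counts each participant once, so participant percentages change less. Ending the window at the next cycle, taken alone, shifts raw counts as much as or more than the present rule for r up to 2.

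A reader might infer that the primary endpoints are double counted. The documents do not support this: protocol 9.3.1 summarizes them for the entire study by dose at onset, and the per-cycle window duplicates nothing there. Nor is a wrong dose column established for 8.2.2 item 4, 8.2.3 item 2 or 11.6, which group by dose before onset.

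**Conclusion.** The point holds as a fault in the written rule: for gaps of 56 days or less, an overlap event is a TEAE of two cycles. The extent of overlap follows from the documents, given six infusions on schedule. The effect on counts rests on an assumed r. The protocol's amendment rationale notes a temporal association of serious headache and aseptic meningitis with infusion, which makes r above 1 plausible for some events but gives no value. The early-restart shares are also unknown.

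The treatment-emergent laboratory period in SAP 8.3 has the same open end. It is affected only if values are not assigned to a cycle by visit: SAP 3.2.1 analyses by scheduled visit, but the markedly abnormal tables also take unscheduled visits.

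Severity is minor to should-fix: the primary tables are untouched, but the rule is wrong as written and cheap to correct.

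**What to change.** - In SAP 8.2.1, and in 8.3 for consistency, assign each TEAE to one cycle: end the window of cycle k at the earlier of 56 days after its last dose and the day before the first dose of cycle k+1. This removes the overlap at every gap and does not touch when a cycle may start. Record it in SAP 3.9 as a change from protocol 9.3.1, and check the 56-day note under the ECG table in 13.6.
- Because early-restart cycles then have shorter windows, show length of follow-up per cycle beside the by-cycle counts. Also produce by cycle the Treatment Period TEAE table, which 8.2.2 item 2 plans for the entire study only. For six-infusion cycles this is the like-for-like comparison.
- In SAP 4.2.2, for AE onsets known only to the month in which a later cycle starts, impute that cycle's first dose date unless it is after the AE stop date. Leave the year-only rule as it is. State which cycle applies if shortened cycles or early restarts put two first doses in one month.

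Cost: a few sentences, a derivation update, one column and one table; no new data. By-cycle tables already produced for the July 2022 submission cut would not match the new definition and would need a note.
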